## 7.2 Dosing Day (Week 1 / Day 1)

Participants who have signed informed consent and have met all the inclusion criteria and none of the exclusion criteria will continue to Day 1.

### Pre-Dose

- Review concomitant medications
- Symptom directed physical exam including weight
- Vital signs after 5 minutes in a supine or seated position (blood pressure, heart rate, temperature, respiration rate)
- Blood and urine samples for serum chemistry, CBC with differential and platelet count, coagulation tests, and urinalysis
- [REDACTED]
- Urine test for pregnancy
- [REDACTED]
- Administration of C-SSRS

### Dose of AT-1501

#### 1-hour infusion

- Vital signs after 5 minutes in a supine or seated position taken at 15 minutes into the infusion (blood pressure, heart rate, temperature, respiration rate)
- AE assessment

### Post Dose

- Assessments performed post-infusion are timed from the end of the 1-hour infusion, not the IV-line flush.
- Vital signs after 5 minutes in a supine or seated position (blood pressure, heart rate, temperature, respiration rate) at 1 and 2 hours post-infusion
- ECG 2 hours post-infusion

█ [REDACTED]

- AE assessments

### 7.3 Phone Call Checks (Weeks 2, 4, 6, 8, 10 and 12; Days 8, 22, 36, 50, 64 and 78 $\pm$ 2 days)

- AE assessment
- Record concomitant medications

### 7.4 Dosing Day (Weeks 3, 5, 7, 9 and 11; Days 15, 29, 43, 57, and 71 $\pm$ 2 days)

#### Pre-Dose

- Symptom directed physical exam (including examination of the injection site and weight)
- Vital signs after 5 minutes in a supine or seated position (blood pressure, heart rate, temperature, respiration rate)
- Record concomitant medications
- Blood and urine samples for serum chemistry, CBC with differential and platelet count, coagulation tests, and urinalysis

█ [REDACTED]

█ [REDACTED]

█ [REDACTED]

- Administration of C-SSRS

█ [REDACTED]

█ [REDACTED]

- AE assessment

## Dose

- 1-hour infusion
- Vital signs after 5 minutes in a supine or seated position and then taken again at 15 minutes into the infusion (blood pressure, heart rate, temperature, respiration rate)
- AE assessment

## Post-Dose

- Assessments performed post-infusion are timed from the end of the 1-hour infusion, not the IV-line flush.
- Vital signs after 5 minutes in a seated position (blood pressure, heart rate, temperature, respiration rate) at 1 and 2 hours post-infusion

█ [REDACTED]

- ECG taken 2 hours post-infusion
- AE Assessment

## 7.5 End of Study (Week 15 ± 1 week)

- Symptom directed physical exam (including examination of the injection site and weight)
- Vital signs after 5 minutes in a supine or seated position (blood pressure, heart rate, temperature, respiration rate)
- Blood and urine sample for serum chemistry, CBC with differential and platelet count, coagulation tests, and urinalysis

█ [REDACTED]

- ECG

█ [REDACTED]

- Administration of C-SSRS
- Record concomitant medications
- AE assessment

## 8 PROCEDURES AND EVALUATIONS

### 8.1 Assessments of Safety

#### 8.1.1 Medical History and Physical Examination

A medical history is obtained through review of the participant's medical records and personal interview in order to assess eligibility. Assessment of eligibility should include a full review of all concomitant medications and relevant vaccinations or immunizations.

A complete physical examination is performed at the screening visit as well as a COVID-19 test to be conducted no later than a week prior to the first infusion. The complete physical examination will include measurement of height, weight and vital signs. A symptom-directed physical examination (including examination of the injection site and weight) and vital signs is performed pre-dose on the days of dosing. Vital signs include heart rate, respiratory rate, blood pressure (after being seated/supine for at least 5 minutes) and temperature.

A weight change of 10% or greater from the previous measurement will warrant a recalculation of the AT-1501 dose.

### 8.1.2 Electrocardiogram

A 12-lead ECG will be obtained locally by a qualified technician and interpreted locally by a qualified physician. ECGs will be obtained at Screening, post-infusion on dosing days and at the End of Study Visit. Post-infusion ECGs should be read on the day they are taken.

### 8.1.3 Columbia Suicide Severity Rating Scale

The Columbia Suicide Severity Rating Scale, or C-SSRS, will be administered at Screening, pre-dose each dosing day and End of Study, by a certified individual. The scale will be used as a prospective assessment for active suicidal ideation with a plan and to identify specific behaviors which may be indicative of a participant's intent to complete suicide.

In order to ensure inter-rater reliability raters will be trained centrally according to a standardized protocol.

### 8.1.4 Clinical Laboratory

Blood samples do not need to be drawn fasting. Blood samples for routine safety labs will be drawn locally, processed and shipped to the following central laboratory for testing. Please refer to the Laboratory Manual for additional details.

Tests to be done may include:

**Serum Chemistry:** sodium, potassium, chloride, magnesium, bilirubin, alkaline phosphatase (ALP), alanine aminotransaminase (ALT), aspartate aminotransferase (AST), Lactate dehydrogenase (LDH), urea, creatinine, phosphorus, calcium, glucose, albumin, total protein.

**Hematology:** CBC (including hematocrit and hemoglobin) with, differential and platelet count, coagulation tests (PT, PTT, INR), fibrinogen, neutrophils, lymphocytes, monocytes, eosinophils, basophils.

**Serum Pregnancy Test** must be performed for women of child-bearing potential. Initial screening results will be used to determine if the participant is eligible for protocol enrollment.

**Blood Tests** for HIV, Hepatitis B surface antigen and Hepatitis C antibody

**Urinalysis:** blood, bilirubin, glucose, ketones, leukocytes, nitrites, pH, protein, specific gravity, urobilinogen, microscopic (bacteria, cast, crystals epithelial cells, mucus, RBC, WBC)

See Appendix A for the Time and Events Schedule and the Laboratory Manual for additional details regarding collection, processing and shipping of samples.

## 8.2 Other Assessments

[REDACTED]

[REDACTED]

[REDACTED]

[REDACTED]

[REDACTED]

[REDACTED]

[REDACTED]

[REDACTED]

[REDACTED]

[REDACTED]

[REDACTED]

[REDACTED]

[REDACTED]

[REDACTED]

## 9 DESCRIPTION OF INVESTIGATIONAL PRODUCT

AT-1501 is supplied as a lyophilized powder in a single use 6mL glass vial with a rubber stopper and flip-off aluminum seal. Each vial contains 40 mg AT-1501 and is intended for single use only.

[REDACTED]

The drug is to be reconstituted in the pharmacy. The reconstituted liquid is clear and will be injected into 100 mL of saline solution for infusion. See the Pharmacy Manual for instructions on reconstitution, storage and preparing the infusion bag.

### 9.1 Sample Vial Label

Labelling will be performed in English at the drug distribution center. See sample label below:

[REDACTED]

[REDACTED]

[REDACTED]

**AT-1501 for IV Use Only**

**Anelixis Therapeutics**

**Single Use Vial**

**Prior to Reconstitution: Store at 2 to 8°C**

**See Pharmacy Manual for reconstitution, use and storage instructions**

**Caution: New Drug Limited by Federal Law to Investigational Use Only**

## **9.2 Drug Ordering and Storage**

AT-1501 is manufactured [REDACTED]. The filled glass vials will be stored for distribution at Fisher Clinical Services. Initial orders will be addressed to the pharmacy, where the vials for use will be stored.

Instructions on reconstitution, use and storage conditions will be provided in the Pharmacy Manual.

## **9.3 Dosage and Administration**

Participants in this study will be enrolled into one of four dose groups: AT-1501 1.0 mg/kg, AT-1501 2.0 mg/kg, AT-1501 4.0 mg/kg, or AT-1501 8.0 mg/kg.

AT-1501 will be given as a 1-hour IV infusion. An IV pump will be used for consistency of delivery. Equipment required for the administration of AT-1501 will be described in the Pharmacy Manual and supplied by the clinical site.

A Pharmacy Manual will be provided to the sites giving instructions on reconstitution by dose and by timing of reconstitution as it relates to dose time.

## **9.4 Drug Accountability**

The study medication will be kept in a secure area of the pharmacy with limited access. It will be supplied to participants in the trial only under the supervision of the Investigator. The Investigator is responsible for drug accountability and maintaining accurate records of the dispensing of study medication. Drug accountability will be performed by a monitor. Used vials will be kept by the clinical site until drug accountability has been completed by the monitor and returned to Fisher Clinical Services, or if authorized, disposed of at the clinical site and documented.

## **10 ADVERSE EVENTS**

### **10.1 Definition of Adverse Events**

An AE is any untoward medical occurrence in a patient or clinical investigation participant administered a pharmaceutical product (which does not necessarily have a causal relationship with this treatment) reported during or after having received the investigational product/procedure. An AE can therefore be any unfavorable and unintended sign (including an abnormal laboratory finding), symptom, or disease temporally associated with the use of an investigational product, whether or not related to the investigational product.

#### **10.1.1 Reporting of Adverse Events**

During the study, the Investigator or clinical site personnel will be responsible for querying and recording adverse events and serious adverse events. Events may be spontaneously reported by the participant, discovered during general questioning by the Investigator, or detected through physical examination, laboratory test or other means. Serious adverse events will be collected from the time of informed consent; all adverse events will be collected from the first administration of investigational product until completion of the final visit and will be evaluated by the Investigator/designee for duration, severity, seriousness, and relationship to investigational product, as outlined below. In addition, the actions taken for the AE will also be documented on the eCRF. Full laboratory data are to be collected in this study, and toxicity trends will be analyzed utilizing objective toxicity criteria.

A baseline recording of any symptoms of illness will be performed before administration of the investigational product. Only symptoms that increase in severity or frequency after investigational product administration or new symptoms of illness will be recorded as AEs. If the event reflects worsening symptoms, then this should be captured in the event term. Untoward medical events which occur after signature of the informed consent but before investigational product administration will be recorded as medical history.

For AEs occurring at the site of infusion the phrase “injection-site” or similar should be included in the event term (e.g. treatment-site erythema). AEs will be evaluated using the Common Terminology Criteria for Adverse Events (CTCAE Version 4.03). All AEs will receive a CTCAE categorization from the Investigator. AEs will also be categorized according to relatedness to the investigational product (see Section 0).

The investigators are responsible for monitoring the safety of patients who have entered this study and for reporting to the Sponsor if serious adverse events (SAE) occur. The Investigator is further responsible for appropriate medical care of patients during the study. The Investigator remains responsible to follow, through an appropriate health care option, AEs that are serious or that caused the patient to discontinue before completing the study. In case of an AE, the patient must be followed until the event resolves or until the Investigator determines the AE has reached a stable outcome or is no longer clinically significant. Frequency of follow-up is left to the discretion of the Investigator. Participant notes throughout the study will be maintained by the Investigator.

### 10.1.2 Assessment of Severity of Adverse Event

All AEs will be assessed using the CTCAE scale as follows:

- Grade 1 Mild; asymptomatic or mild symptoms; clinical or diagnostic observations only; intervention not indicated.
- Grade 2 Moderate; minimal, local or noninvasive intervention indicated; limiting age-appropriate instrumental Activities of Daily Living (ADL).
- Grade 3 Severe or medically significant but not immediately life-threatening; hospitalization or prolongation of hospitalization indicated; disabling; limiting self-care ADL.
- Grade 4 Life-threatening consequences; urgent intervention indicated
- Grade 5 Death related to AE

### 10.1.3 Onset of Adverse Events

The Investigator will classify the onset of each AE relative to the following stages of treatment:

- During AT-1501 infusion
- After AT-1501 infusion

### 10.1.4 Relationship of Adverse Event to Investigational Product

The Investigator's assessment of the relationship of the AE(s) to the investigational drug will be assessed as Not Related, Unlikely, Possible or Probable. For these purposes, the following definitions will be used:

- Not Related:** A clinical event, including laboratory test abnormality, with a temporal relationship to drug administration which makes a causal relationship improbable, and in which other drugs, chemicals, or underlying disease provide plausible explanations.
- Unlikely:** A clinical event, including laboratory test abnormality, with a temporal relationship to drug administration which makes a causal relationship unlikely, and in which other drugs, chemicals or underlying disease provide plausible explanations.
- Possible:** A clinical event, including laboratory test abnormality, with a reasonable time sequence to administration of the drug, but which could also be explained by concurrent disease or other drugs or chemicals. Information on drug withdrawal may be lacking or unclear.
- Probable:** A clinical event, including laboratory test abnormality, with a reasonable time sequence to administration of the drug, unlikely to be attributed to concurrent disease or other chemicals, and which follows a clinically reasonable response on withdrawal.

**Related:** An AE that is almost certainly related to the use of the study drug. The AE cannot be reasonably explained by an alternative explanation, e.g., concomitant drug(s), concomitant disease(s).

For purposes of assigning relatedness – Not Related and Unlikely will be considered NOT RELATED. Possible, Probable and Related will be considered RELATED.

## **10.2 Serious Adverse Events**

### **10.2.1 Definition of a Serious Adverse Event**

A SAE is an adverse event occurring at any dose that results in any of the following outcomes:

- Death
- Life-threatening
- Persistent or significant disability/incapacity
- Prompts a hospital admission or prolongs hospitalization
- Congenital anomaly/birth defect
- Important medical events

Important medical events that may not result in death, be life-threatening, or require hospitalization may be considered serious adverse events when, based upon appropriate medical judgment, they may jeopardize the participant and may require medical or surgical intervention to prevent one of the outcomes listed above. AEs that do not result in any of these outcomes are considered non-serious.

Participants should be closely followed for AEs during the study. Whether or not the adverse events are considered related to the investigational product, they must be reported.

SAEs occurring more than 4 weeks after a patient's last dose of AT-1501 will NOT be reported unless the Investigator feels that the event may have been caused by the investigational product or a protocol procedure.

Pregnancies occurring within the 3-month period after the last treatment, and coming to the attention of the Investigator, should be followed to document any congenital anomalies or birth defects, should they occur. For purposes of consistency, pregnancies will be recorded in the SAE System; however, the event will then be downgraded if the outcome does not meet the SAE criteria.

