## 5 INVESTIGATIONAL TRIAL DESIGN

### 5.1 Design

[figure not shown]
This is a Phase 2a, multi-center, open label, multiple dose study of AT-1501, a humanized monoclonal antibody antagonist to CD40LG. Approximately 54 adults with ALS will be enrolled into the study in the United States at up to 12 ALS treatment sites in the United States and 1 site in Canada.

Four ascending doses of AT-1501 (1.0 mg/kg; 2.0 mg/kg, 4.0 mg/kg and 8.0 mg/kg) will be administered as a 1-hour IV infusion to sequentially enrolling cohorts. The 1.0 mg/kg and 2.0 mg/kg cohorts will consist of 9 participants each and the 4.0 mg/kg and 8.0 mg/kg cohorts will consist of 18 participants each. The participants in each cohort will receive 6 bi-weekly (every other week) infusions of AT-1501 over an 11-week period.

The primary objective of the study is to assess safety and tolerability.

[REDACTED]

This study consists of a 4-week screening period, an 11-week dosing period in which participants are dosed once every other week, and a 4 week follow-up period. On Day 1 eligible participants will receive their first 1-hour intravenous (IV) infusion of AT-1501 and will be observed for at least 2 hours post infusion before being released. They will return for clinical visits on Weeks 3, 5, 7, 9 and 11 for subsequent infusions and will remain at the clinical site for at least 2 hours for observation and assessments before being released. Participants will be called weekly between dosing visits (Weeks 2, 4, 6, 8, 10 and 12) by a member of the research team to record adverse events (AE) and changes in concomitant medications. Participants will be followed for an additional 4 weeks after their last dose to monitor for safety, with an end of study clinic visit occurring Week 15.

Each participant will be monitored for safety throughout the study. Safety will be assessed by evaluation of AEs, changes in safety laboratory parameters, physical examination including vital signs, ECGs and the Columbia Suicide Severity Rating Scale (C-SSRS).

The dose limiting toxicity observation period to determine the safety of a dose level is defined as starting with administration of the first dose of AT-1501 to the first participant in a cohort through the administration of the second dose of AT-1501 in the 6th participant in that cohort (See 10.3 for Stopping Rules and Dose Limiting Toxicity).

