#### **6.2 Participant Screening**

The purpose of Screening Visit 1 is to thoroughly inform, both verbally and in writing, the potential participant about the study and allow him/her the opportunity to ask questions. The potential participant will then sign and date the informed consent form and screening procedures can be performed. Once the consent form is signed the participant is considered enrolled into the study and any serious adverse events that occur will be captured from the date of consent until the end of study participation.

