## 6.6 Study Drug Discontinuation

Participants may be discontinued from receiving study drug for any of the following reasons:

- Lack of cooperation with study requirements;

- Intercurrent illness, that in the opinion of the Investigator, would unreasonably increase the risks of the study procedures, or otherwise compromise the safety of the participant or the integrity of study results;
- Participant refuses further treatment with AT-1501;
- Actions taken to control the -spread of COVID-19 (e.g. no access to study drug)
- Active COVID-19 infection
- Participant Withdraws consent to the trial;
- Stopping rules are met;
- At the direction of Anelixis;
- At the direction of the Investigator.

The effects of AT-1501 have not been studied in patients that have been diagnosed with COVID-19. It is unknown whether taking the investigational drug will increase or decrease the risk of getting COVID-19 or the effect it may have on the clinical course of a participant who develops COVID-19. Potential participants for the study will be tested for COVID-19 prior to entering the study. If a participant tests positive they will not be allowed to participate in the study. If a participant is diagnosed with COVID-19 while receiving treatment in this study, the administration of the investigational drug will be stopped, and appropriate medical care and follow-up will be done. The participant will continue to be monitored for safety.

All participants that withdraw from treatment with AT-1501 for any reason should continue to be followed until the end of study.

If at any time during the study a participant experiences an adverse event the Investigator believes is severe enough to preclude further AT-1501 administration or the stopping rules are met the participant will be discontinued from study drug treatment and will receive medical treatment as determined by the Investigator. The participant will be followed until the event resolves or until the Investigator determines the AE has reached a stable outcome or is no longer clinically significant. Regardless, each participant will be followed for safety for at least 4 weeks from the last AT-1501 infusion. A final visit will be completed according to the end-of-study evaluation (Section 7.6).

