### **10.2.2 Reporting of Serious Adverse Events**

All SAEs, whether or not thought related to the investigational product, must be reported by the Investigator or designee (by telephone, fax or email) [REDACTED] within 24 hours of the Investigator becoming aware of the event. The Investigator or responsible clinical site staff will complete and submit the Serious Adverse Event report form and then enter all adverse events into the eCRF.

Serious adverse event reports should be sent to:

Following receipt of the SAE report, the Safety group will review the report and contact the Investigator to request additional information or for data clarification. Redacted medical records supporting the event should be submitted as they become available. For all SAEs occurring during the study, the Investigator must submit follow-up reports [REDACTED] [REDACTED] regarding the participant's subsequent course until the SAE has resolved, reached a stable outcome, or is no longer clinically significant. The timelines and procedure for follow-up reports are the same as those for the initial report. The submitted reports must be retained by the site.

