13.1 Adverse Events

An AE is any untoward medical occurrence in a subject or clinical investigation subject administered a pharmaceutical product (which does not necessarily have a causal relationship with this treatment) reported during or after having received the investigational drug/procedure. An AE can therefore be any unfavorable and unintended sign (including an abnormal laboratory finding), symptom, or disease

temporally associated with the use of an investigational product (IP), whether or not related to the IP. Treatment-emergent adverse events (TEAEs) are defined as any event that occurs or worsens on or after the first dose of study medication. All TEAEs will be collected from the first administration of IP until completion of the final visit.

A serious adverse event (SAE) is an AE that results in any of the following outcomes: death, life-threatening, persistent, or significant disability/incapacity, prompts a hospital admission or prolongs hospitalization, congenital anomaly/birth defect, or other important medical events. All SAEs will be collected from the time of informed consent until completion of the final visit.

All AEs will be evaluated by the Investigator/designee for duration, severity, seriousness, and relationship to investigational product. In addition, the actions taken for the AE will also be documented on the eCRF. Only symptoms that increase in severity or frequency after IP administration or new symptoms of illness will be recorded as AEs in the eCRF. If the event reflects worsening symptoms, then this should be captured in the event term. Untoward medical events which occur after signature of the informed consent but before IP administration will be recorded as medical history.

Serious adverse events recorded in the eCRF which began prior to the first dose of study medication will not be included in the summary tables but will be included in the AE data listings. AEs will be coded using MedDRA Version 23.1. Severity of AEs will be assessed as Grade 1 (lowest severity) to 5 (highest severity) using the National Cancer Institute Common Terminology Criteria for Adverse Events (NCI-CTCAE) Version 4.03. Relationship to study drug will be categorized as Not Related, Unlikely, Possible, Probable, and Related. Related AEs will be classified as those categorized as Probable, Possible, Related; or those missing an assessment of relationship to study drug.

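### Protocol 10.2.1 ends reporting of SAEs judged unrelated 4 weeks after the last dose; Protocol 6.2, 10.1.1 and SAP 13.1 run to the end of participation or final visit

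*Protocol*

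**What the plan says.** Protocol 10.2.1 limits SAE reporting by time since last dose: "SAEs occurring more than 4 weeks after a patient's last dose of AT-1501 will NOT be reported unless the Investigator feels" that the event may be due to the product or to a protocol procedure. Just before this, the same section says that adverse events must be reported whether or not they are considered related.

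Three other places set a longer window without a causality condition:

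- Protocol 6.2: "any serious adverse events that occur will be captured from the date of consent until the end of study participation".
- Protocol 10.1.1: SAEs are collected from consent, and "all adverse events will be collected from the first administration of investigational product until completion of the final visit".
- SAP 13.1: "All SAEs will be collected from the time of informed consent until completion of the final visit".

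Protocol 10.2.2 adds "All SAEs, whether or not thought related to the investigational product, must be reported by the Investigator or designee" within 24 hours. It gives no end date, so 10.2.1 can be read as its exception; those two sections are in tension rather than in direct conflict.

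On follow-up, Protocol 5.1 plans that "Participants will be followed for an additional 4 weeks after their last dose to monitor for safety". For participants who stop drug, Protocol 6.6 says "All participants that withdraw from treatment with AT-1501 for any reason should continue to be followed until the end of study". For discontinuation because of an adverse event or a stopping rule, it adds a minimum: "each participant will be followed for safety for at least 4 weeks from the last AT-1501 infusion".

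**The concern.** The 4-week limit in 10.2.1 fits a participant who receives all six infusions, since planned follow-up is also 4 weeks. It does not fit one who stops drug early and is followed to the end of study. That participant's limit is counted from an early dose and can expire well before the final visit. Read literally, the rules then produce an odd result: a non-serious event in the gap is collected under 10.1.1, while an SAE on the same day that is judged unrelated is not reported.

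Safety is the primary endpoint, and SAEs by system organ class and preferred term is a topline table (SAP 18, Table 14.3.1.4). Anyone dosed once is in the Safety Analysis Set, and the treatment-emergent definition in SAP 13.1 has no upper limit tied to the last dose, so these events belong in the tables. If sites carry the 10.2.1 limit over to the eCRF, late SAEs enter only when the investigator suspects the product or a procedure. The SAE table and the summary of TEAEs leading to death could then be incomplete. An event that was never recorded cannot have its causality reassessed later.

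Early stopping is foreseeable. Protocol 6.5 provides for replacing participants who leave before four doses, and Protocol 6.6 stops drug on a COVID-19 diagnosis while safety monitoring continues.

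**Working it through.** The documents give no figure for the mismatch, so it is derived here from the visit schedule.

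**Inputs**

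- Dosing days 1, 15, 29, 43, 57 and 71, with ±2 days on all but Day 1 (Protocol 7.4, Appendix A).
- Final visit on Day 101 ±7 days (Protocol Appendix A; SAP Table 2).
- Alternative anchor of Day 99. By the protocol's own numbering week *w* starts on Day 7(*w* − 1) + 1 (Week 11 = Day 71, Week 12 = Day 78), so Week 15 starts on Day 99.
- Cut-off under 10.2.1 = day of last dose + 28.

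**Formulas**

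- Nominal gap = final visit day − (last dose day + 28). Example for one dose: 101 − (1 + 28) = 72 days.
- Low end with windows, using Day 99: max(0, 92 − (cut-off + 2)).
- High end with windows, using Day 101: 108 − (cut-off − 2).
- The ±2 is dropped for dose 1.

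| Last dose | Dose day | Cut-off day | Gap to Day 101 | Gap to Day 99 | Range with windows |
|---|---|---|---|---|---|
| 1 | 1 | 29 | 72 | 70 | 63–79 |
| 2 | 15 | 43 | 58 | 56 | 47–67 |
| 3 | 29 | 57 | 44 | 42 | 33–53 |
| 4 | 43 | 71 | 30 | 28 | 19–39 |
| 5 | 57 | 85 | 16 | 14 | 5–25 |
| 6 (completer) | 71 | 99 | 2 | 0 | 0–11 |

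With Day 101 alone as anchor, the low ends for doses 1 to 5 rise by 2 days, to 65, 49, 35, 21 and 7.

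**Share of observation time.** After one dose, 72 of the 100 days from dosing to Day 101 fall after the cut-off. For a completer it is 2 of 30.

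**Scheduled adverse event contacts after the cut-off** (Day 101 final visit):

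- Full schedule kept: 8, 6, 4, 2 and 1 after last dose 1 to 5.
- Only phone calls and the final visit kept: 5, 4, 3, 2 and 1.

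The protocol does not say which schedule applies after drug is stopped.

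**Who carries the gap in total.** Per participant, early stoppers clearly do (16–72 days against 2). In total person-days it depends on a stopping rate that the documents do not give. As an assumption, spread early stops evenly over doses 1 to 5 and follow all of them to Day 101:

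- Mean gap = (72 + 58 + 44 + 30 + 16)/5 = 44 days.
- Early stoppers hold half of the affected person-days when the stopping rate is 2/(44 + 2) = 4.3%, or 2.3 of 54, so 3 or more stoppers hold the majority.
- At stopping rates of 5%, 10% and 20% their share is 54%, 71% and 85%.
- If every completer had the maximum 11-day gap, break-even would be 11/(44 + 11) = 20%.

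**Low case.** If follow-up after an adverse event or stopping rule ends at the 4-week minimum in 6.6, the gap is near 0.

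**The case against.** The strongest reply is that the passages govern different things. Section 10.2.1 limits what is *reported*, and 10.2.2 describes reporting as the 24-hour notice and SAE form. The longer windows speak of events being *captured* or *collected*. On that reading only the expedited report stops at 4 weeks and the eCRF stays complete. The wording of 10.1.1, and the unconditional instruction in 10.2.2 to enter all adverse events in the eCRF, favour it.

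There are also safeguards:

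- Events go in the medical chart, with 100% source data verification (Protocol 12.2).
- The monitor compares the participant record with the CRF and queries missing entries (Protocol 13.6).
- All adverse events are assessed at scheduled contacts (Appendix A).
- Death appears as a reason for discontinuation in the disposition table (SAP 9).

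Finally, the group is narrow. Participants who withdraw consent are asked to complete the end-of-study evaluation at their next scheduled contact (Protocol 6.5), so during dosing their gap is about zero. Only SAEs judged unrelated to both product and procedure are at stake, so drug-related SAE summaries are unaffected.

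The narrowing stands, and the safeguards lower the risk. The reconciliation is plausible, but no passage states it. The lines just before the limit in 10.2.1 use *reported* for all adverse events, and 10.2.2 places eCRF entry after the report form, so a site told not to report could skip both. A monitor who reads 10.2.1 as a valid exclusion would have no reason to query the omission. The SAP's claim to supersede the protocol covers statistical methods, not collection rules.

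**Conclusion.** The concern holds. Followed literally, 10.2.1 drops SAEs that 6.2, 10.1.1 and SAP 13.1 keep, and no passage ranks the rules. The mismatch is nominally 16 to 72 days for a participant who stops after dose 1 to 5, retains consent and is followed to Day 101 (5 to 79 days over both final-visit anchors with visit windows). For a completer it is 0 or 2 days nominally and at most 11.

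That the conflict exists is certain. That SAEs would be lost from the tables is conditional on sites applying 10.2.1 to the eCRF, and the number lost cannot be computed without SAE and discontinuation rates. SAEs thought possibly caused by product or procedure are kept on either reading. This should be fixed, because the rule bears on a primary-endpoint table and the correction is small.

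**What to change.** Amend Protocol 10.2.1 to agree with 6.2, 10.1.1 and SAP 13.1: all SAEs, whatever their judged causality, are recorded in the eCRF and reported through the participant's final visit, and the possible-causation condition applies only to SAEs after that visit. If the sponsor meant to limit only the 24-hour report, 10.2.1 should say so and state that eCRF recording continues to the final visit. That lesser change is enough to protect the tables.

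The cost is one sentence in a protocol amendment, re-instruction of up to 13 sites (12 in the United States, 1 in Canada) and, under the first option, whatever additional SAE reports arise. The SAP needs no change, because SAP 13.1 already states the final-visit window.
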